Best model selection. We will select best models using the unbiased Bayesian Information Criterion (BIC) and use 10-fold cross-validation to protect against overfitting the model. To deal with potentially high-dimensional phenotype variables and other demographic and clinical covariates, regularized regressions will be considered. Penalties in the likelihood function will follow the Elastic Nets family with LASSO favored for its feature elimination potential. Alternative machine-learning model-free algorithms (random forests, SVMs) will be utilized for comparison, using the binary form of the response variables.

Characterizing the predictive performance. Cross-validated and BIC-based measures of explained variation will be used to characterize the predictive potential of the continuous response models. This analysis will be supplemented with ROC analysis based on the binary form of the response variables. We will use the cross-validated and kernel-smoothed area under the ROC curve (AUC) as an appealing measure of the predictive potential with good interpretability. Order effects will be considered during secondary analysis.

Causal analysis. We will conduct exploratory analysis of causal relationships between the light and deep phenotypic factors and the analgesic and secondary response variables. We are interested in particular causal analyses potentially implicating neurobiological and inflammatory biomarkers (deep phenotyping variables) as having a mechanistic role in the mediation of the treatment effects of light phenotypic measures. Specifically, we will measure the potential mediation effect of the deep phenotype biomarkers as the proportion of the treatment effect (PTE) explained by the biomarker. PTE is represented by a relative change in the treatment regression coefficients when the biomarker is included in the model relative to the coefficient before inclusion. We will use bootstrap methods to estimate standard errors for the proportion of explained treatment effects. Wald test statistic of the form (change in regression coefficient)/(bootstrap Standard Error) will be used to test for the presence of the mediation effect.

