Handling protocol deviations. Participant-specific protocol deviations will be assessed for their potential relationship to the treatment effects or the course of the disease by a medical expert. Since deviations because of safety will generally result in incomplete data on the subject, their consequences will be handled in the analysis as potentially informative missing data (as described above). Because of the difficulty of accurate determination of the relationship between protocol deviations and the treatment efficacy and the disease dynamics, several versions of the primary and secondary analysis will be undertaken:

Exclusion of the violators from the analysis population under the missing at random assumption.

1. Single (if, as expected, missing data fraction does not exceed 15%) or multiple imputation of the violator's unobserved responses using predictive matching algorithms, including the per-protocol analysis of the resultant imputed population(s).
2. With yes/no responses that have the meaning of success or failure where mixed logistic models are used per protocol, violator's responses will be classified as failures for the conservative analysis.
3. Analytic methods (2,3) applied only to violators classified as treatment or disease-related as defined by medical experts.

Power for explaining treatment effects. Consider a regression model correlating within-patient improvement due to one of the 4 main treatments with a phenotypic variable. Using a two-sided test for correlation at 5% significance level we conclude that we will have the power of at least 86% to detect correlation of 0.3 or higher, conservatively assuming the model is applied to one randomized treatment segment with 100 patients. This corresponds to first phase or second phase treatment in one of the 4 treatment groups, and a model based on the light phenotyping patient group of 400 total. Similar analysis for the smaller subgroup based on 40 patients with available deep phenotyping for a specific treatment and segment shows that correlation of 0.43 or higher will be detectable with 81% power. This is well within reach as evidenced by available literature on the association between treatment effects and phenotype variables. For example, mindfulness and pain responses showed correlations of 0.43-0.51 in prior reported studies. Our previous studies of the association between pain centralization and analgesic responses in knee OA showed similar or higher correlations.

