Power for prediction. We expect that at least 30% of patients will show 50% improvements in analgesic outcomes under each of the treatments. We expect the predictive panel of light phenotypic variables to show AUC exceeding a clinically relevant AUC of 0.7, dependent on the specific setting. Under this assumption we will have the power of at least 91% to reject the null hypothesis AUC of 0.5 by a two-sided test in the subgroup analysis setting described above. With the panel including the deep phenotyping variables we expect to be able to reach a better AUC of 0.8 or higher. However, the analysis is based on smaller size of the subgroup (40 vs. 100). This results in the power of at least 89% for a similar test of AUC.

Go/no-go decisions to recommend model-based predictor panel for future clinical use. We are targeting a high sensitivity of the predictive panel of 80%. Under this scenario, the cross-validated ROC curve will be kernel-smoothed, and the decision threshold will be determined from the smoothed data to meet the 80% sensitivity. Under a normal approximation to the panel score distribution for patients who show 50% improvement and the ones who do not, in the hypothetical scenario of the above power calculation, we assess that the expected specificity value at 80% sensitivity will be around 50%. To provide guidance at the end of the study as to whether the panel is worth recommending for use in the clinical setting, worth a further study or non-promising, we will consider the overall rate of correct decisions. With the targeted sensitivity and specificity and the expected pain improvement rate in the subgroup, we are expecting that the decision will be at least 41%

correct overall. We will consider the assay not useful if it has the true overall correct decision rate of 25% or less. Dependent on the outcome, the panel will be potentially considered worth of further pursuit in the sense of potentially doubling the sample size in a future study and having a non-ambiguous decision at the end with Type I and type II errors of 5% each. Using the Fleming sequential testing design we conclude that with less than 13 correct predictions of improvement under treatment at the end of the current study the panel will be considered not worth pursuing. With 21 or more correct decisions, the biomarker will be considered clinically relevant, and with the number of correct decisions between 13 and 21, we will consider the biomarker worth of further study.

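### The 91% and 89% power for the prediction panel is the power of one score fixed in advance and makes no allowance for fitting and cross-validating the panel in the same patients

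*Protocol*

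**What the plan says.** All of this is in Protocol 18.1.5.

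- **Power for prediction.** The responder assumption is: "We expect that at least 30% of patients will show 50% improvements in analgesic outcomes under each of the treatments". For the light panel: "We expect the predictive panel of light phenotypic variables to show AUC exceeding a clinically relevant AUC of 0.7", and then "Under this assumption we will have the power of at least 91% to reject the null hypothesis AUC of 0.5 by a two-sided test". The setting is one treatment segment of 100 patients. For the panel with deep variables the AUC is 0.8 or higher in 40 patients: "This results in the power of at least 89% for a similar test of AUC". No formula, standard error or panel size is given.
- **Best model selection.** Models are chosen by BIC, with elastic-net or LASSO penalties considered for high-dimensional phenotypes. The analysts will "use 10-fold cross-validation to protect against overfitting the model".
- **Characterizing the predictive performance.** "We will use the cross-validated and kernel-smoothed area under the ROC curve (AUC) as an appealing measure" of predictive potential.
- **Go/no-go decisions.** The decision threshold is read from the cross-validated, smoothed ROC curve.

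SAP Section 6 gives power for correlations only. The SAP contains no AUC test and no AUC power that would replace the protocol figures.

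**The concern.** A power formula for an AUC treats the score as known before the data are seen. Here the weights, and possibly the choice of variables, are estimated from about 30 responders (light) or 12 (deep), and the result is judged by cross-validation in the same patients. Three things then change:

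- The fitted panel discriminates less well than the best possible one.
- The cross-validated AUC varies more than the AUC of a fixed score.
- With no association at all, it is not centred on 0.5.

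This holds even when every fitting step stays inside the folds, so it is separate from any leakage through earlier variable selection. These two figures are the only power stated for the prediction objective. If they are too high, a useful panel will be missed more often than the plan says.

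**Working it through.** **Inputs.** From Power for prediction: 30% responders, so 30 and 70 of 100, or 12 and 28 of 40; AUC 0.7 or 0.8; a two-sided test against 0.5. The significance level is not restated there and is taken from the correlation power paragraph: "Using a two-sided test for correlation at 5% significance level". Panel size is not given. SAP Table 2 lists two light variables per arm and seven distinct ones. For MBSR and PT, one of the two is labelled a moderator and the other a mediator. SAP Table 3 lists three or four deep variables per arm.

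**Step 1: reproduce the stated figures for a fixed score.** With m responders and k non-responders, the Hanley-McNeil variance is

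Var = [A(1−A) + (m−1)(U−A²) + (k−1)(V−A²)] / (mk), where U = A/(2−A) and V = 2A²/(1+A).

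The null SE is √[(m+k+1)/(12mk)].

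- Light: U = 0.538, V = 0.576. Var = (0.21 + 29×0.0485 + 69×0.0865)/2100 = 0.00361, so SE = 0.0601. Null SE = √(101/25200) = 0.0633. Power = Φ[(0.2 − 1.96×0.0633)/0.0601] = Φ(1.263) = 89.7%. With the alternative SE throughout, Φ(0.2/0.0601 − 1.96) = 91.4%.
- Deep: U = 0.667, V = 0.711. Var = (0.16 + 11×0.0267 + 27×0.0711)/336 = 0.00706, so SE = 0.08404. Null SE = √(41/4032) = 0.10084. Power = Φ[(0.3 − 1.96×0.10084)/0.08404] = Φ(1.218) = 88.8%.

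The binormal (Obuchowski) variance gives 90.7% and 89.3%. Direct simulation of a fixed score gives 90.4-91.2% and 90.1-90.7%. The plan's figures are therefore fixed-score power.

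**Step 2: what fitting and cross-validation change.** These results are simulated with equal-variance normal predictors, 30% responders and the panel refitted inside each of 10 folds.

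- Lost discrimination: with a best-possible AUC of 0.80 and n = 40, the fitted panel's true AUC is 0.783 with 2 predictors, 0.755 with 4 and 0.729 with 6.
- A lower statistic: when the fitted two-predictor panel truly has AUC 0.700 (n = 100), the pooled cross-validated AUC averages 0.688. At 0.801 (n = 40) it averages 0.772.
- A different null: the cross-validated AUC centres at 0.46-0.49. Its SD is 0.089-0.093 at n = 100 (formula 0.063) and 0.137-0.146 at n = 40 (formula 0.101).

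**Step 3: power of the cross-validated AUC.** *Ordinary* means a test with a standard AUC standard error. *Calibrated* means a cut-off at the 97.5th percentile of the simulated null. Most cells have 2,000 runs; some fitted-panel cells have 1,500, the fixed-penalty L1 fit has 1,000 and the tuned LASSO has 150. Ranges span fitting methods.

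| Setting (stated power) | 0.7/0.8 is the best possible panel | 0.7/0.8 is the fitted panel, out of sample |
|---|---|---|
| Light, 2 predictors (91%) | ordinary 77-83%; 71-72% with unstratified folds and pooled AUC; 69-71% with tuned LASSO; calibrated 73-76% | ordinary 84-89%; calibrated 80-82% |
| Light, 7 predictors (91%) | ordinary 62-67%; calibrated 50-53% (L1 fit lower: 58% and 43%) | ordinary 81-89%; calibrated 73-74% |
| Deep, 4 predictors (89%) | ordinary 61-75%; calibrated 49-65% | ordinary 81-86%; calibrated 75-76% |
| Deep, 7 predictors (89%) | ordinary 55-67%; calibrated 37-51% | ordinary 80-86%; calibrated 69-72% |

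No cell in the table reaches the stated figure. The seven-predictor light rows are illustrative: the seven variables belong to the SAP's all-arm model, not to one arm.

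**Step 4: error with no association.** The ordinary two-sided z-test rejects about 15-20% of the time. Most of these rejections lie below 0.5; the upper tail is about 4-6% instead of 2.5%.

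**The case against.** **The arithmetic is right.** It is: the figures follow from the stated inputs. The issue is which statistic they describe.

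**The plan never says that the 91% and 89% test is applied to the cross-validated AUC.** That is an inference. However, no other AUC is defined for the panel, and the go/no-go paragraph also works from the cross-validated curve.

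**The expected AUC may already be the fitted panel's own.** The wording allows this. Power under an ordinary test is then nearly flat in panel size (83-87% for 2 to 10 light predictors in one set of runs). A reader might infer that larger panels always lose power, or that the shortfall is at least ten points. Neither follows from the documents. The first holds if 0.7/0.8 is the best-panel AUC, or under a calibrated cut-off. The second also depends on that choice, and the plan names no such cut-off.

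**The inputs are floors.** True, but a claim of at least 91% has to hold at the floor, and the fixed-score formula gives 91% exactly there.

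**The analysis is exploratory, and other models pool arms.** Protocol 18.1 is headed as exploratory. SAP 9.1.1 and 9.2 fit T3 and T4 across all arms, and SAP 7.5 prefers confidence intervals to p-values. This lowers the stakes. It does not change the one-segment setting that the protocol chose for its power statement.

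**Conclusion.** The point holds in a limited form: the stated power is for a fixed score and leaves out the cost of building and cross-validating the panel. On the best-panel reading the loss is large: roughly 70-83% with two light predictors, 50-67% with seven, and 50-75% with four deep predictors. On the fitted-panel reading it may be only a few points: roughly 80-89% (light) and 75-87% (deep) with few predictors. The documents do not settle which reading applies. The ranges rest on normal predictors, 30% responders and assumed panel sizes. Kernel smoothing was not simulated.

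Two stronger conclusions are not supported. A reader might take the 15-20% null rejection rate as the rate at which worthless panels are declared useful. Most of those rejections are below 0.5, and the plan does not name the standard error that produces them. A reader might also conclude that the go/no-go cut-offs of 13 and 21 correct decisions fail. They come from a Fleming design on counts; only the expected specificity of about 50% uses the same scenario as the AUC power.

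**What to change.** In Protocol 18.1.5, Power for prediction:

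1. State the number of candidate variables in the light panel and in the panel with deep variables, the fitting method and the fold scheme.
2. Say whether 0.7 and 0.8 are the AUC of the ideal panel or the out-of-sample AUC of the fitted one.
3. Replace 91% and 89% with power simulated for the full procedure (selection, penalised fitting, 10-fold cross-validation and smoothing) at n = 100 and n = 40 with 30% responders. The ranges above are illustrative and should not be inserted as the new figures.
4. Test AUC = 0.5 with a permutation test that repeats the whole fitting and cross-validation pipeline for each permuted set of labels. Protocol 10.2.1 already uses label permutation for the SVM models.

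The cost is revised wording, a short simulation and some computing time. The stated power becomes less favourable. No extra patients or visits are needed.

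### Go/no-go rule for the predictor panel: the 41% is not the overall correct rate that its inputs give, the 25% limit lies below chance, and the cut-offs 13 and 21 have no stated denominator

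*Protocol*

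**What the plan says.** All of this stands in Protocol 18.1.5, in the paragraphs on power for prediction and on go/no-go decisions.

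- Improver rate: "We expect that at least 30% of patients will show 50% improvements in analgesic outcomes under each of the treatments".
- Operating point: the threshold is set for 80% sensitivity, and under a normal approximation the "expected specificity value at 80% sensitivity will be around 50"%.
- Metric: "we will consider the overall rate of correct decisions".
- Expected value: "we are expecting that the decision will be at least 41"% correct overall.
- Null: "We will consider the assay not useful if it has the true overall correct decision rate of 25% or less".
- Errors: "a non-ambiguous decision at the end with Type I and type II errors of 5% each", allowing for a possible doubling of the sample in a later study.
- Cut-offs from a Fleming design: the panel is dropped "with less than 13 correct predictions of improvement under treatment at the end of the current study". At the other end, "With 21 or more correct decisions, the biomarker will be considered clinically relevant". Counts in between mean further study.

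The only group sizes given in this setting are 100 (light phenotyping) and 40 (deep phenotyping) per treatment. The SAP repeats the correlation power calculation, with 102 and 40, but not this rule.

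**The concern.** A rule of this kind needs three things: a defined proportion, a null that represents a useless panel, and a denominator for the counts. Here the expected value does not agree with the named proportion. The null looks too low, because a score without information still gets some decisions right once it is forced to 80% sensitivity. The counted event is first described as a correct prediction of improvement and then as a correct decision, which are different events with different denominators. A reader at the end of the study could not apply the rule without guessing, and a panel no better than chance would not be filtered by it. At stake is the protocol's guidance on whether a panel is ready for clinical use, merits more study or should be dropped.

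**Working it through.** **Inputs** (Protocol 18.1.5): improver rate p = 0.30; sensitivity Se = 0.80; specificity Sp about 0.50; AUC 0.7 (light) and 0.8 (deep); null 0.25; errors 5% each; sample doubled.

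**1. The 41%.**

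- Overall correct = p·Se + (1−p)·Sp = 0.3×0.8 + 0.7×0.5 = 0.24 + 0.35 = 0.59.
- PPV = p·Se / [p·Se + (1−p)(1−Sp)] = 0.24 / (0.24 + 0.35) = 0.407. This reproduces the stated figure.
- 0.41 is also 1 − 0.59, the overall error rate. PPV fits better: the text counts correct predictions of improvement, and PPV rises with the improver rate, as the words at least require, while the error rate falls.

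Binormal specificity is Φ(√2·z(AUC) − z(0.80)):

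| Panel | Specificity | Overall correct | PPV |
|---|---|---|---|
| Stated specificity | 0.50 | 59.0% | 40.7% |
| Light, AUC 0.7 | 0.460 | 56.2% | 38.8% |
| Deep, AUC 0.8 | 0.636 | 68.5% | 48.5% |
| Uninformative, AUC 0.5 | 0.20 | 38.0% | 30.0% |

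**2. The null.** For an uninformative panel at 80% sensitivity, overall correct is 0.8p + 0.2(1−p) = 0.2 + 0.6p, and PPV is p. At p = 0.30 these are 0.38 and 0.30, both above 0.25. A higher improver rate raises both. The limit would equal chance only at p = 0.25 for PPV, or p = 0.05/0.6 = 0.083 for overall accuracy. Both are below the expected minimum of 0.30.

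**3. The cut-offs.** Fleming's first-stage bounds for n of a possible 2n, with p0 = 0.25 and z = 1.645:

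- Upper: n·p0 + z√(2n·p0(1−p0)), rounded, plus 1.
- Lower: n·pA − z√(2n·pA(1−pA)), rounded, where pA = (√(2n·p0) + z√(1−p0))² / (2n + z²).

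| n | Lower / upper before rounding | Cut-offs, nearest integer |
|---|---|---|
| 40 | 9.55 / 16.37 | ≤10, ≥17 |
| 50 | 12.03 / 19.62 | ≤12, ≥21 |
| 51 | 12.28 / 19.94 | ≤12, ≥21 |
| 52 | 12.52 / 20.26 | ≤13, ≥21 |
| 59 | 14.26 / 22.49 | ≤14, ≥23 |
| 100 | 24.47 / 35.07 | ≤24, ≥36 |

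The protocol's pair (≤12, ≥21) appears at n = 50 and 51. With floor rounding it appears at 52 and 53 instead. Under a PPV reading the denominator is the number of predicted improvers, about 59 of 100, and that does not return the pair either.

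**4. Illustration.** Take n fixed at 50 and a final cut-off of 33 of 100 from the same formula (2n·p0 + z√(2n·p0(1−p0)) = 32.1, rounded, plus 1); the protocol states no final cut-off. Exact binomial probability of being called relevant by the end of the doubled study: 4.5% at a true rate of 25%, 29% at 30%, and 95% at 40.7%.

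**The case against.** **The low null is covered elsewhere.** The same section plans a two-sided test of AUC against 0.5, with stated power of at least 91% and 89%, and uses cross-validated performance. That test does address an uninformative panel, so it would be wrong to say that the protocol has no safeguard. But the go/no-go rule is not made conditional on it, and cross-validation does not raise a null that is set below chance. The criticism stands for the counting rule on its own.

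**The figures cohere as PPV with n = 50.** They do: the two-stage error is 4.5% at 25%, and the power is 95% at 40.7%. About 50 predicted improvers can even be reached from stated figures: 100 patients less the 15% ceiling for missing data, times 0.59, is 50.15. So a reader might infer that 13 and 21 contradict the group sizes of 40 and 100. The documents do not support that, because they never attach the counts to those groups. What stands is that the denominator is undocumented. Relabelling as PPV also leaves the null below chance.

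**The 5% is delivered.** A reader might set the 29% against the stated 5% as a broken error rate. That is not like for like. The 5% is defined at a true rate of 25%, where the rule meets it. The 29% belongs to a true rate of 30%, and needs an assumed final cut-off and a second study that the protocol calls only potential. The fixed n = 50 is a simplification too: 85 patients with an uninformative panel at 80% sensitivity would yield 68 predicted improvers, and the chance of 21 or more correct is then 48% at the first stage, against 4.8% with 50.

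**Conclusion.** Wrong as written, and minor. Three statements hold on the protocol's own inputs.

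- The overall correct rate is 59% (56% with the binormal specificity at AUC 0.7, 68.5% for the deep panel at AUC 0.8), not 41%. Whether the label or the calculation is at fault cannot be settled from the documents; PPV is the closer match.
- At 30% improvers and 80% sensitivity, the 25% limit is below chance on either metric: 13 points below for overall accuracy (38%) and 5 points below for PPV (30%). The 5% type I error therefore holds only against a panel worse than uninformative.
- The cut-offs imply a denominator of about 50 that is nowhere stated; the exact value depends on the rounding rule.

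The probabilities are plain binomials and ignore that the threshold is chosen on the same data. The rule falls under exploratory mechanistic analysis, the SAP omits it, and no primary, secondary or safety decision rests on it.

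**What to change.** Name one metric and its denominator.

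- **If overall accuracy:** restate 41% as about 56–59% for the light panel and about 69% for the deep panel, with all evaluable patients as the denominator.
- **If PPV:** relabel the figure and state that the denominator is the number of predicted improvers, which varies with the panel (59 of 100 at the expected specificity, 80 of 100 for an uninformative panel).

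Set the null no lower than chance for that metric: 0.2 + 0.6 × improver rate for overall accuracy, or the improver rate itself for PPV. Recompute both cut-offs and the delivered error rates for the light group (100, or 102 in the SAP) and the deep group (40). For example, overall accuracy against 38% gives ≤38 / ≥50 at n = 100, ≤39 / ≥51 at n = 102 and ≤15 / ≥23 at n = 40. If the rule is no longer intended, say that it is withdrawn.

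The cost is wording and recalculation. The downside is that fewer panels will be called relevant. Against 38% overall accuracy, the first-stage probability is 91% at n = 100 with AUC 0.7 and 95% at n = 40 with AUC 0.8, but 50% if the deep panel reaches only 0.7. Against a PPV of 30%, with 59 predicted improvers and a true PPV of 40.7%, it is 25% at the first stage and 74% after doubling.

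### The go/no-go count for the predictor panel is labelled two ways with no denominator; neither label separates panels at 100 patients, and only one does at 40

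*Protocol*

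**What the plan says.** The rule is in the protocol, section 18.1.5, in the paragraph on go/no-go decisions. It starts from a sensitivity goal, "We are targeting a high sensitivity of the predictive panel of 80" per cent, and sets the cut-off on the study's own cross-validated, kernel-smoothed ROC curve: "the decision threshold will be determined from the smoothed data to meet the 80% sensitivity". For the scenario used in the power calculation, "the expected specificity value at 80% sensitivity will be around 50" per cent.

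The panel is then to be judged on its overall share of correct decisions. This is expected to be at least 41%, and a true share of 25% or less counts as not useful. A Fleming design with 5% error rates turns this into two limits. The lower one reads "with less than 13 correct predictions of improvement under treatment at the end of the current study the panel will be considered" not worth pursuing. The upper one reads "With 21 or more correct decisions, the biomarker will be considered clinically relevant". Counts in between mean further study.

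No number of patients or decisions is attached to 13 or 21. The neighbouring power paragraphs use 100 patients per treatment segment for the light panel and 40 for the deep panel. The SAP does not contain the rule.

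**The concern.** A correct prediction of improvement is a true positive. Once the cut-off has been placed so that 80% of improvers are flagged, the number of true positives is about 80% of the improvers by construction. At fixed sensitivity a good panel differs from a poor one only in its false positives, and a count of true positives does not see them. It mainly records how many patients got better.

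A correct decision is something else: it also includes the patients rightly called non-improvers. That count does respond to specificity. The limits of 13 and 21 carry one label each, as if the two counts were the same.

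The rule decides whether a panel is recommended for clinical use, studied further or dropped. It should therefore be able to fail a panel that carries no information.

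**Working it through.** **Inputs, all from protocol section 18.1.5.** Sensitivity 0.80. Improvement rate 0.30 ("at least 30% of patients will show 50% improvements in analgesic outcomes under each of the treatments"). Light panel: "AUC exceeding a clinically relevant AUC of 0.7", n = 100. Deep panel: "a better AUC of 0.8 or higher", n = 40. Limits: below 13, and 21 or more.

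**The plan's own figures.** With equal-variance normal scores, specificity at 80% sensitivity is Φ(√2·z(AUC) − z(0.80)). At AUC 0.7 this is Φ(0.742 − 0.842) = 0.46, consistent with the stated value of about 50%. The overall share correct is 0.3 × 0.80 + 0.7 × specificity. With specificity 0.50 it is 0.24 + 0.35 = 59%, not 41%. The value 41% is the positive predictive value, 0.24 / (0.24 + 0.35) = 40.7%, or the error rate, 1 − 0.59. Limits of 13 and 21 come out of a two-stage Fleming design with p0 = 0.25 and z = 1.645 only if the first stage holds 52–53 decisions, a number the protocol does not give. The upper limit would be 36 for 100 decisions and 17 for 40.

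**Expected values by AUC**

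| AUC | Specificity | Overall share correct |
|---|---|---|
| 0.5 | 0.20 | 0.24 + 0.14 = 38% |
| 0.7 | 0.46 | 0.24 + 0.32 = 56% |
| 0.8 | 0.64 | 0.24 + 0.45 = 69% |
| 0.95 | 0.93 | 0.24 + 0.65 = 89% |

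Expected true positives are 0.8 × 0.3 × n, which is 24 of 100 or 9.6 of 40 on every row. An uninformative panel is already right 38% of the time, above the 25% limit for a panel that is not useful.

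**Simulation.** Improvers are Binomial(n, 0.3). Scores are normal at the given AUC. The cut-off is the improver score that flags 80% of improvers, rounded up.

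| Count | n | Result | AUC 0.5 | 0.7 | 0.8 | 0.95 |
|---|---|---|---|---|---|---|
| True positives | 100 | P(≥21) | 84% | 84% | 84% | about 84% |
| True positives | 40 | P(<13) | about 88% | about 88% | about 88% | about 88% |
| All correct calls | 100 | P(≥21) | 99.9% | 100% | 100% | 100% |
| All correct calls | 40 | P(≥21) | 18% | 73% | 93% | 100% |

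The mean true-positive count is 24.4 at n = 100 and 10.0 at n = 40, at every AUC. Among all correct calls, the AUC 0.5 panel averages 39 at n = 100. At n = 40 it falls below 13 about 17% of the time.

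**Sensitivity to how the cut-off is set.** With a kernel-smoothed cut-off, P(true positives ≥21) at n = 100 is 87–88% from AUC 0.5 to 0.99. At n = 40, P(all correct ≥21) is 9%, 60% and 88% at AUC 0.5, 0.7 and 0.8, and 100% at 0.99; the useless panel falls below 13 in 25% of trials. The pattern is the same.

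**The case against.** The strongest reply is that true positives are not the intended count. The paragraph introduces the metric as overall correctness, states the 25% limit in those terms, and words both the upper limit and the middle zone as correct decisions. Correct predictions of improvement appear once, at the lower limit. On that reading true negatives count, so false positives do affect the result. This stands. A reader might infer that the rule is blind to panel quality however it is read; the documents do not support that, because the overall count separates panels at 40 patients.

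It does not rescue the rule for the light panel. At 100 patients the overall count exceeds 21 for essentially any panel. Nor does the text settle on this reading: the expected 41% matches the positive predictive value and not the overall share.

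A third reading takes 13 and 21 out of a fixed 52–53 predicted improvers. That would discriminate, with 7–9% reaching 21 at AUC 0.5 against 100% at 0.99. But the protocol does not give that denominator, and it cannot be held fixed: at n = 100 and 80% sensitivity a panel flags about 80 patients at AUC 0.5 and about 25 at AUC 0.99.

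It is also fair to say that the stakes are limited. The rule is offered as guidance in a section headed as exploratory. Discrimination is assessed separately, by a test of AUC against 0.5 and by cross-validated AUC. A reader might infer that the trial's main conclusions are at risk; they are not.

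**Conclusion.** The point holds in conditional form. The protocol gives one decision count two labels and no denominator. As true positives, the count cannot separate panels at either sample size: about 84% reach 21 at n = 100, and about 88% fall below 13 at n = 40, regardless of AUC. On that label the light panel usually passes and the deep panel is usually dropped, whatever their merit. As all correct decisions, the count cannot separate panels at n = 100, where a coin-flip panel passes in 99.9% of trials. At n = 40 it does separate them, but rarely drops a useless one.

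Correcting the 41% or adding a denominator would not cure the true-positive version; the statistic itself has to change. The figures assume equal-variance normal scores, a true improvement rate of 30%, one treatment segment, and a cut-off chosen in the data in which the count is taken. This should be changed, but it does not touch the primary or secondary endpoints.

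**What to change.** Replace the 13/21 count with the cross-validated specificity at the 80% sensitivity cut-off, the quantity that varies between panels once sensitivity is fixed. Obtain confidence bounds by bootstrapping the whole cross-validation, including the choice of cut-off. Judge specificity against 20%, the value for an uninformative panel, and make a lower bound above 20% the minimum condition for a go.

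Do not also require a point estimate of at least 50%. The protocol's AUC 0.7 scenario implies about 46%, so the design-target panel would usually miss. In a simulation of 400 trials without model fitting, a rule with that requirement gave a go about 34% of the time at n = 100 and 31% at n = 40. The sponsor should set the upper target from its own scenario and state the operating characteristics at both sample sizes. The expected overall share should be corrected to 59% if it is kept, and the rule should be carried into the SAP.

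The cost is wording plus a modest simulation. The downside is that the rule can now fail: a go becomes less likely, and at n = 40 the bounds are wide, so further study will be a common outcome.
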